Appendix 4. Guides for In-depth Interviews

Tools for data collection: Guides for in-depth Interviews

General information:

Identification #:

Interview location:

Name of Interviewer:

Date:

Start time:

End time:

Interview 1: Questions for In- school Adolescent girls (In-depth Interviews)

Participant: Adolescent girl currently attending school

Approximate time required: 1 hour

Introductory questions:

What is your name?

How old are you?

What is your caste or tribe?

What is the highest level of education you completed?

Are you engaged/married?

Who is the head of your family?

How many siblings do you have? Sex, and age?

Main questions:

Decision making

Increasingly girls are able to stay at school, but sometimes girls have to leave. Could you please tell me a bit about what happens in your family? Who is involved in making major decisions about your life, such as whether you stay at school, or get married? Probe: explore role of men and women in the family in decision making.

Education

Many girls in your community do not get a chance to go beyond class 7, how did you stay on to study beyond class 7th? Probe: Motivations and barriers.

Is there any form of help that would enable you to stay in school for longer?

Do you know of the government schemes in your school? Do you think that the ones you availed help you stay in school?

Do girls in your community seek higher education – up to 12th, college? What happens if girls get higher education up to 12th or college? What happens when girls do not get higher education or drop out from school?

Do you believe girls should be encouraged to get higher education? Up to 12th, Up to college or above? Do you believe boys should be encouraged to get higher education?

Do you think others in the community believe girls should be encouraged to get higher education? Probe: Who are these important people? Do you think others in the community believe boys should be encouraged to get higher education?

Do you know about the laws/ policies supporting girl child education?

Marriage

Do girls in your community get married early? Who are the people in the community (or family) who take decision on a girl's marriage?

What do you think is the right age for a girl to get married? Probe: Why do you think so? What is the earliest age you would want to get married? Do you believe others in the community expect girls to get married early? Probes: What happens to girls who do not get married early in your community? What happens to girls who get married early in your community?

Sex work

Do girls in your community drop out of school because they get dedicated to Devadasi (muttu ceremony)? Do you know what circumstances made them into a Devadasi's?

Do you believe that girls should be dedicated to Devadasi tradition and drop out of school early?

Do you believe others in the community expect girls to be dedicated to the Devadasi tradition and drop out of school? What do you think will happen if the girl is not dedicated

Entry into workforce

What do you want to become when you grow up? Probe: Do you want to work or be at home? What kind of work do you think you will like to do? What support do you need to fulfill this dream of yours?

Will your family be happy with your choice of work? Probe: what does your father, mother, brother, uncle, grandparent want you to do when you grow up?

How common is it for a girl of your age to be working? Sub questions: Are they your friends? What do you think will be the kind of work that these girls might get into at their age?

Wrap up questions:

Many thanks for all of your help. Is there any other information about you that you think would be useful for me to know? For example, on girls education, marriage or work?

Do you have any suggestions or recommendations to the AG program so as to reach more AG?

Interview 2: Questions for out-of-school Adolescent girls (In-depth Interviews)

Participant: Adolescent girl currently not attending school

Approximate time required: 1 hour

Introductory questions:

What is your name?

How old are you?

What is your caste or tribe?

What is the highest level of education you completed?

Are you engaged/married?

Who is the head of your family?

How many siblings do you have? Sex, and age?

Main questions:

Decision making

Increasingly girls are able to stay at school, but sometimes girls have to leave. Could you please tell me a bit about what happens in your family? Who is involved in making major decisions about your life, such as whether you stay at school, or get married? Probe: explore role of men and women in the family in decision making.

Why did you leave school? Can you please tell me what happened?

Probes: support at school? Home/ resources? Commute?

In the end, who had most influence over this decision?

Education

Thinking back, do you think it was/is right time for you to leave school? Probe: Is there any form of help that would have helped you to stay in school for longer?

Are you aware of government schemes in your school? Did you avail these schemes? Do you think these schemes are attractive/ would have helped you stay in school?

Have you ever considered going back to school? What would help you to go back to school?

Have most of your friends of your age stayed in school, or left? Why do you think this is? Are these girls married?

How has your situation changed, now that you have left school? How do you usually spend your day?

Do girls in your community seek higher education – up to 12th, college? What happens if girls get higher education up to 12th or college? What happens when girls do not get higher education or drop out from school?

Do you believe girls should be encouraged to get higher education? Up to 12th, Up to college or above? Do you believe boys should be encouraged to get higher education?

Do you think others in the community believe girls should be encouraged to get higher education? Probe: Who are these important people? Do you think others in the community believe boys should be encouraged to get higher education?

Do you know about the laws/ policies supporting girl child education?

Marriage

Do girls in your community get married early? Who are the people in the community (or family) who take decision on a girl's marriage?

What do you think is the right age for a girl to get married? Probe: Why do you think so? What is the earliest age you would want to get married? Do you believe others in the community expect girls to get married early? Probes: What happens to girls who do not get married early in your community? What happens to girls who get married early in your community?

Sex work

Do girls in your community drop out of school because they get dedicated to Devadasi (muttu ceremony)? Do you know what circumstances made them into a Devadasi's?

Do you believe that girls should be dedicated to Devadasi tradition and drop out of school early?

Do you believe others in the community expect girls to be dedicated to the Devadasi tradition and drop out of school? What do you think will happen if the girl is not dedicated

Entry into workforce

What do you want to become when you grow up? Probe: Do you want to work or be at home? What kind of work do you think you will like to do? What support do you need to fulfill this dream of yours?

Will your family be happy with your choice of work? Probe: what does your father, mother, brother, uncle, grandparent want you to do when you grow up?

How common is it for a girl of your age to be working? Sub questions: Are they your friends? What do you think will be the kind of work that these girls might get into at their age?

Wrap up questions:

Many thanks for all of your help. Is there any other information about you that you think would be useful for me to know? For example, on girls education, marriage or work?

Do you have any suggestions or recommendations to the AG program so as to reach more AG?

Interview 3: Questions for parents/guardians of adolescent girls (In-depth Interviews)

Participant: Parents/guardians, either or both together, of adolescent girls

Approximate time required: 1 hour

Introductory questions:

What is your name?

How are you related to the girl (if not her parents)

How many boys and how many girls do you have?

How old are they?

What is your caste or tribe?

Can you read and/or write?

What is the highest level of education you completed?

Main questions:

Decision-making

In your home, who is involved in making major decisions about things like education and marriage for your children?

How many of your children are of school age? Have you faced any problems in keeping them in school? Have you been able to overcome any of the barriers/challenges?

Are the problems the same for your boys and your girls? Probe: How do you try to resolve these?

Education

What do you think are the main concerns in continuing education for adolescent girls in your locality? Have you had or seen any such experiences that you may want to share with us?

What are other problems girls of your daughter's age have that may affect their studies? (Maybe like health, alcoholism, and lack of entertainment areas etc)

Do you know of any government education schemes in the schools? Does your daughter avail these? Do you think these schemes are any good in keeping girls in school?

Do girls in your community seek higher education – up to 12th, college? What happens if girls get higher education up to 12th or college? What happens when girls do not get higher education or drop out from school?

Do you believe girls should be encouraged to get higher education? Up to 12th, Up to college or above? Do you believe boys should be encouraged to get higher education?

Do you think others in the community believe girls should be encouraged to get higher education? Probe: Who are these important people? Do you think others in the community believe boys should be encouraged to get higher education?

Do you know about the laws/ policies supporting girl child education?

Do you think your daughter should study till that age? Why do you think so? How would you feel if your daughter wished to study till college? What do you think your family and community will think?

Marriage

Do girls in your community get married early? Who are the people in the community (or family) who take decision on a girl's marriage?

What do you think is the right age for a girl to get married? Probe: Why do you think so? At what age will you want your daughters to be married?

Do you believe others in the community expect girls to get married early? Probes: What happens to girls who do not get married early in your community? What happens to girls who get married early in your community?

Sex work

Do girls in your community drop out of school because they get dedicated to Devadasi (muttu ceremony)? Do you know what circumstances made them into a Devadasi's?

Do you believe that girls should be dedicated to Devadasi tradition and drop out of school early?

Do you believe others in the community expect girls to be dedicated to the Devadasi tradition and drop out of school? What do you think will happen if the girl is not dedicated

Entry into workforce

What do you want your daughter to do when she grows up? Probe: Do you want her to work or be at home? What kind of work do you think she will like to do? What support do you need to fulfill this dream of hers?

Will your family be happy with your choice of work? Probe: what does your father, mother, brother, uncle, grandparent want you to do when you grow up?

How common is it for a girl of your daughter's age to be working? Sub questions: What do you think will be the kind of work that these girls might get into at their age?

Wrap up questions:

Many thanks for all of your help. Is there any other information about you that you think would be useful for me to know?

Do you have any suggestions or recommendations to the AG program so as to reach more AG?

Interview 4: Questions for teachers (In-depth Interviews)

Participant: School teachers of adolescent girls or girls and boys

Approximate time required: 1 hour

Introductory questions:

What is your name?

Where do you teach?

How old are the kids that you teach? How many girls/boys are in your class?

What subjects do you teach?

Have you been given any training for life skills education or gender sensitization?

Main questions:

Decision-making

Thinking about children in your school, who is it who makes the decisions about whether girls or boys stay or continue in school?

Do you think girls have a say on whether or not they stay in school, or the age they get married at?

Education

What do you see as being the main factors that lead to girls leaving school early? Probe: problems in school? Family problems?

Is the situation very different for girls, than for boys? Probes: support at school? finances/resources? Tuitions? Eve-teasing? Distance? Commute?

Probe: Can you please give me an example?

Are there other problems that girls in your school area have that may affect the education of these girls? (maybe like health, alcoholism, and lack of entertainment areas etc) (Sub question: Why/Why not?)

How does your school try to overcome the challenges? Probe: Can you please give me an example?

Do you know of any government education schemes in the schools? Do you think these schemes are any good in keeping girls in school?

Do you have any suggestions about how girls could be helped to stay on in school?

Do girls in your community seek higher education – upto 12th, college? What happens if girls get higher education up to 12th or college? What happens when girls do not get higher education or drop out from school?

Do you believe girls should be encouraged to get higher education? Upto 12th, Upto college or above? Do you believe boys should be encouraged to get higher education?

Do you think others in the community believe girls should be encouraged to get higher education? Probe: Who are these important people? Do you think others in the community believe boys should be encouraged to get higher education?

Do you know about the laws/ policies supporting girl child education?

Marriage

Do girls in your community get married early? Who are the people in the community (or family) who take decision on a girls marriage?

What do you think is the right age for a girl to get married? Probe: Why do you think so? Do you believe others in the community expect girls to get married early? Probes: What happens to girls who do not get married early in your community? What happens to girls who get married early in your community?

Sex work

Do girls in your community drop out of school because they get dedicated to devadasi (muttu ceremony)? Do you know what circumstances made them into a Devadasi's?

Do you believe that girls should be dedicated to Devadasi tradition and drop out of school early?

Do you believe others in the community expect girls to be dedicated to the devadasi tradition and drop out of school? What do you think will happen if the girl is not dedicated?

Entry into workforce

What do you want your girl students to do when they grow up? Probe: What kind of work do you think they will do and are able to do?

Do you speak to them about this?

When do you think your girl or boy should start working? Sub questions: Do you know children that are working? What works do they do? What do you think will be the kind of work that these girls might get into at their age?

Wrap up questions:

Many thanks for all of your help. Is there anything else that you would like to add? Any particular opinions on leaving education? Marriage or working?

Do you have any suggestions or recommendations to the AG program so as to reach more AG?

Interview 5: *Questions for Adolescent boys*

Participant: Adolescent boys currently residing in the intervention villages

Introductory questions:

What is your name?

How old are you?

What is your caste or tribe?

What is the highest level of education you completed?

Are you engaged/married?

Who is the head of your family?

How many siblings do you have? Sex, and age?

Main questions:

Decision making

Thinking about adolescent girls and boys in your locality, who is it who makes the decisions about whether girls or boys stay or continue in school?

Do you think girls have a say on whether or not they stay in school, or the age they get married at? How does it happen in your family?

What about boys? Do they have a say about staying in school? When and whom to marry?

If different from girls, how do you explain this (why do you think this is?)

Do you think boys/girls should be involved in decision making?

Education

Many girls in your community do not get a chance to go beyond class 7 (while more boys do), what do you think will be the reasons for this? Probe: Motivations and barriers.

Is the situation very different for girls than for boys? Can you please give some examples? (If nothing forthcoming) Probe: support at school? finance/ resources/ tuition/ distance of commuting?

Do girls in your community seek higher education – up to 12th, college? Do you know any? How are they different from girls who do not continue or drop out from school?

Do you believe girls should be encouraged to get higher education? Up to 12th, Up to college or above? Do you believe boys should be encouraged to get higher education? Explain a little more

Who in the community (and family?) would encourage higher education for boys/girls? Who in the community/family would want to oppose this?

What would change for boys if more girls would go for higher education (or when girls are treated in the same ways as boys in terms of education)? Anything positive? Any negative consequences for boys?

What level of education do you think you will attain? (Up to 12th? College? Who will decide? Will you have a say in that)

What level of education do you think your sister (cousin sister) will achieve? Up to 12th? College? Who will be involved in deciding this?

Do you know girls in your community who drop out of school because they get dedicated to Devadasi (muttu ceremony)? How were they different from other girls? Do you know what circumstances made them into a Devadasi's?

Have you heard about any laws/ policies supporting girl child education?

Marriage

At what age do girls in your community get married? What do you think is the right age for a girl to get married? Why do you think so?

Do you believe others in the community expect girls to get married early (before 18)?
Probes: What happens to girls who do not get married early in your community? What happens to girls who get married early in your community?

Thinking about your future and when you will get married. Would you like your future wife to be educated? upto 12th? College? Tell me why you think this?

Support

I would like to understand how boys and girls in your locality relate. Are boys supportive of girls? Do you think boys can support girls? How can they do that?

What do you see your role is as a brother? (consider sisters, if no sisters, ask about cousin sisters). Can you think of a situation where they needed your support? What was it? What did you do?

Do you you feel a duty to 'protect' your sister? Would they support them not to get married?

In your locality, do boys tease girls? Which girls in particular?

Will boys tease their sisters and cousin sisters? Will boys tolerate their sisters being teased by other boys? Can you tell me about yourself and your sisters? Can you protect her in any way not to be teased? How? What would you do?

Entry into workforce

When do you think a girl or boy should start working (for money)? Sub questions: Do you know adolescent boys or girls that are working? What kind of work do they do? What do you think will be the kind of work that these girls might get into at their age?

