1. Proportion of SC/ST girls in the cohort(s) who pass their matric/class 10 exam
2. Proportion of SC/ST girls in the study cohort who report a change in attitude around gender equality
3. Proportion of SC/ST girls in the study cohort who access available government schemes to assist SC/ST girls to complete secondary school
4. Proportion of SC/ST girls in the study cohort who access tuition classes and/or career counselling at school
5. Proportion of SC/ST girls in the study cohort who have experienced one or more incidents of harassment by boys in the last 3 months: in school; on the way to school; elsewhere in the community.

Process level outcomes

Process level outcomes are intended to understand the pathways from the intervention to the primary and secondary outcomes. They include data collected from the adolescent girls, their families, their schools, and communities:

Adolescent girls:

1. Awareness of the government schemes/subsidies that encourage their education
2. Attendance in tutorial classes
3. Participation in Parivartan Plus group sessions
4. Participation in career counseling to enhance options after school completion
5. Shifts in attitudes and perceived norms among SC/ST girls in the study cohorts and their parents about the value of completing secondary education for girls.
6. Shifts in attitudes and perceived norms among study girl parents about the wisdom of marrying girls before age 18.
7. Shift in attitudes and perceived norms among SC/ST girls in the study cohorts and their parents regarding [some measure of gender equality taken from Parivartan curriculum for boys]
8. Absences from school among the study cohort and proportion of adolescent girls who successfully pass into the next grade (the last element of this outcome would need to be measured using monitoring data for girls not in the cohorts).

Schools/SDMCs/Teachers:

1. Proportion of schools that have developed and implemented action plans to encourage entry and retention of girls in secondary school
2. Proportion of schools that have developed and implemented action plans to make schools safer for girls (anti-harassment, safe toilets, etc)
3. Proportion of surveyed teachers who feel that secondary school education is easily accessible for SC/ST girls in their community
4. Proportion of surveyed teachers who feel that SC/ST girls in their community have the opportunity to continue and complete their secondary

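### Appendix 4 interview guides: the dedication question joins two attitudes in one, early marriage has a stated age only in the boys' guide, and two further items are leading or misaddressed

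*Protocol*

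**What the plan says.** The protocol's section on in-depth interviews plans semi-structured, open-ended interviews in years one and four with girls, families, teachers, boys and community leaders. For girls, parents, teachers and boys it names prevailing norms on gender, education and marriage as a focus. The Qualitative research section says such interviews are meant to examine change in the community. The guides are in Appendix 4; five are shown.

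- **Dedication.** Interviews 1 to 4 (in-school girls, out-of-school girls, parents, teachers) ask "Do you believe that girls should be dedicated to Devadasi tradition and drop out of school early" and then "Do you believe others in the community expect girls to be dedicated to the Devadasi tradition and drop out of school".
- **Early marriage.** Interviews 1 to 4 ask "Do girls in your community get married early" and whether others expect it, with no age. Interview 5 (boys) asks "Do you believe others in the community expect girls to get married early (before 18", where the bracket supplies the age, and separately asks at what age local girls marry. Process level outcome 6 for adolescent girls also uses 18, for parents' views on "the wisdom of marrying girls before age 18". All five guides ask "What do you think is the right age for a girl to get married".
- **Schooling, boys.** Interview 5 opens with "Many girls in your community do not get a chance to go beyond class 7 (while more boys do". After asking for the reasons, it asks whether the situation is very different for girls than for boys.
- **Work, parents.** Interview 3 first asks what the parent wants the daughter to do. It then asks whether the family will be happy with the respondent's own choice of work, with the probe "what does your father, mother, brother, uncle, grandparent want you to do when you grow up".

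**The concern.** Dedication is part of the trial's rationale, and age of entry into sex work is in study question 2. A question that merges approval of dedication with approval of leaving school gives an ambiguous answer on the topic for which the protocol lists least other information. A respondent could come to favour schooling while still accepting dedication, or the reverse, and the answer to this item alone would not show it.

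The other three items raise a similar problem on a smaller scale. If early means different ages to different groups, or its meaning shifts between year one and year four, answers about what the community does or expects are hard to compare. A premise that already says more boys than girls continue makes the following question less informative. A probe addressed to the wrong person fails to collect what it was meant to collect.

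The timetable labels the interviews with girls, families, teachers and boys as intervention-area interviews, and Interview 5 specifies boys living in intervention villages. The contrast between rounds therefore carries much of the weight, and clear, consistent wording helps it.

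**Working it through.** There is no figure in the plan to reproduce; the check is a comparison of texts.

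1. **What the dedication item can distinguish.** There are two attitudes, each accepted or rejected, so 2 × 2 = 4 positions. Read literally, yes fits one of them (accept both). No fits the other three: reject dedication only, reject leaving school only, reject both. The expectation item has the same structure. No separating probe is written beside either, although the guides write probes elsewhere, for instance after the right-age question.

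2. **Whether another source covers it.** In Tables 4 and 5, Devadasi status appears only as a family demographic. Entry into sex work in Table 4 concerns the girl's own experience, not her attitude. Table 6 lists a gender scale for the school survey but no dedication domain. The process outcomes for girls, families and communities name norms on marriage and education, not dedication. Appendix 2 refers to separate questionnaires that are not shown, so this comparison covers listed domains only.

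3. **What early means in each guide.** In Interviews 1 to 4, both the practice question and the expectation question leave it undefined. In Interview 5, practice is asked as an open age and expectation is tied to 18. The wording therefore differs between boys and everyone else on both. The right-age question is common to all five guides, but it records the respondent's own view, not what the community does or what others expect.

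4. **Order of the boys' schooling questions.** The statement that more boys than girls go beyond class 7 comes before the question whether their situations differ. Interview 3 shows a more neutral form already in use: it asks parents whether the problems are the same for their boys and girls.

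5. **Parents' work questions.** The opening question is correctly about the daughter. The next question and its probe match the girls' guides, so the parent is asked what the parent's own relatives want the parent to do on growing up. Parents are therefore not asked what the daughter's other relatives want for her.

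6. **Interviews touched, by planned numbers per round.** Dedication and early marriage: 10 in-school girls + 10 out-of-school girls + 10 families + 10 teachers = 40. Boys' schooling item: 20. Parents' work item: 10. The protocol allows these numbers to rise if saturation is not reached.

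**The case against.** The strongest reply is that these are topic guides, which the protocol itself calls probe lists, and not scored questionnaires. Answers are open and analysed by theme, so a competent interviewer who hears no can ask what is being rejected. The dedication items are also flanked by questions on the circumstances of dedication and on what happens if a girl is not dedicated. The Data collection section says instruments will be piloted and revised, in a general sentence placed in the questionnaire paragraph. All of this stands and limits the harm. It does not remove the case for writing the separation into the guide, because otherwise it depends on each interviewer in each round.

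A reader might infer that change in norms cannot be read from the interviews at all. The documents do not support that. Every guide shown asks the right age to marry. Girls are asked the earliest age they would want to marry, and parents the age they want for their daughters. Encouragement of higher education is asked separately for girls and boys. Marriage and education norms are also a domain of the structured family survey, in both arms at baseline and follow-up.

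Three further inferences should be resisted:

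- The planning drop-out range of 9% to 17% from 7th to 8th standard does not show the class 7 premise to be false. The protocol calls those figures conservative and elsewhere reports 34% of girls from devadasi families leaving school by age 10. The defect is that the premise suggests an answer. For in-school girls a similar premise leads into how the girl herself stayed on, which is a different question.
- The misaddressed probe does not mean that family expectations about work are lost. Parents state their own wishes, and girls are asked what their relatives want.
- No percentage can be put on the loss. The design estimates no proportions from these interviews, so invented shares answering yes would not fit it.

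**Conclusion.** The point holds as a minor improvement to the wording of the qualitative instruments. The dedication item is its main part: as written, an unprobed answer does not separate dedication from leaving school, and no other listed domain covers attitudes to dedication. Answers on early marriage as community practice or expectation are not directly comparable between boys and the other groups; the right-age question makes up for this only in part. The boys' schooling item suggests its answer, and the parents' work item misses other relatives' wishes for the daughter.

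This rests on the guides being used broadly as printed and on the unseen questionnaires adding no dedication attitudes beyond the domains in Tables 4 to 6. If either assumption fails, the point weakens further. Primary outcomes, sample size and error rates are unaffected.

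**What to change.** Change four places in Appendix 4:

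1. **Interviews 1 to 4, dedication.** Ask two questions: *Should girls be dedicated?* and *If a girl is dedicated, should she leave school?* Ask each for own belief and for what others in the community expect.
2. **All guides, marriage.** In place of early, ask openly at what age girls in the community marry and at what age others expect them to marry. Copying the boys' age of 18 into the other guides would supply a benchmark, so open ages are preferable. Keep the right-age question.
3. **Interview 5, schooling.** Drop the premise and ask *Do girls here usually go on after class 7? And boys?*
4. **Interview 3, work.** Ask what the daughter's father, mother and other relatives want her to do.

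The cost is a few lines of guide text and their translation, with no extra interviews. If year one has already been done, the reworded items will differ between rounds, and their year-four answers should be reported separately and not as change from year one.
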